5.2. Determination of Sample Size

Approximately 240 patients will be randomized to 1 of 4 double-blind treatment regimens to evaluate the primary endpoint. Patients will be randomized to placebo, 50 mg LY3074828 Therapeutic Drug Monitoring (TDM), 200 mg LY3074828 TDM, or the 600 mg LY3074828 fixed-dose treatment group in a 1:1:1:1 ratio (60 patients per arm). The randomized patients will be comprised of approximately one-third biologic-naïve patients (~20 per arm) and approximately two thirds patients who have been exposed previously to at least 1 biologic agent (~40 per arm).

Assuming LY3074828 and placebo clinical remission rates of 30% and 7.5% respectively (a difference of 22.5%) and given 60 patients per treatment arm, each pairwise comparison testing

the superiority of LY3074828 to placebo will have 89% power via chi-square test with a two-sided 0.05 significance level.

5.3. Method of Assignment to Treatment

Patients who meet all criteria for enrollment will be randomized to treatment at the baseline visit. Assignment to treatment groups will be determined by a computer-generated random sequence using an interactive web-response system (IWRS), and then the site will be responsible for administering the treatment to the patients.

Patients will be randomized into the Induction Dosing Period at a 1:1:1:1 ratio to one of four treatment groups, each given as one IV injection:

- 600 mg LY3074828 IV Q4W: A dose of 600 mg given as an IV infusion at Weeks 0, 4, and 8.
- 200 mg LY3074828 IV TDM Q4W: A dose of 200 mg TDM given as an IV infusion at Weeks 0, 4, and 8. Dose adjustments may occur at Week 4 and 8.
- 50 mg LY3074828 IV TDM Q4W: A dose of 50 mg TDM given as an IV infusion at Weeks 0, 4, and 8. Dose adjustments may occur at Week 4 and 8.
- Placebo: A dose of placebo saline given as IV injections at Weeks 0, 4, and 8.

Patients who have clinical responses to LY3074828 (as defined in section 6.11.3.1) at the end of the Induction Dosing Period will be re-randomized to 1 of 2 maintenance LY3074828 treatment arms in the Maintenance Dosing period. This randomization will be stratified according to the patient's Week 12 remission status.

- 200 mg SC LY3074828 Q4W: A dose of 200 mg given as a SC injection at 4 week intervals starting at week 12.
- 200 mg SC LY3074828 Q12W: A dose of 200 mg given as a SC injection at 12 week intervals starting at week 12.

Patients who have clinical responses to placebo (as defined in section 6.11.3.1) at the end of the Induction Dosing Period will continue to receive placebo via SC injection in the Maintenance Dosing period. Placebo responders will not be re-randomized.

Patients who do not have clinical responses to LY3074828 (as defined in section 6.11.3.1) at the end of the Induction Dosing Period will have the option to continue on to the Extension Period-Induction portion of the trial. Patients entering the Extension Period-Induction portion of the trial will not be re-randomized but will receive 1000 mg LY3074828 given as an IV infusion at extension weeks 0, 4, and 8.

Patients who have clinical responses to LY3074828 (as defined in section 6.11.3.1) at the end of the Extension Period-Induction will continue to the Extension Period-Maintenance portion of the trial. Patients entering the Extension Period-Maintenance portion of the trial will not be re-randomized but will receive 200 mg LY3074828 given as a subcutaneous (SC) injection at 4 week intervals starting at extension week 12.

6. A Priori Statistical Methods

6.1. General Considerations

Eli Lilly and Co. will be responsible for conducting the statistical analysis and for the generation, validation and final production of the Efficacy and Health Outcomes tables, figures and listings (TFLs) proposed in this document. Robarts Clinical Trials, a clinical research organization, will be responsible for conducting the statistical analysis and for the generation, validation and final production of all other tables, figures and listings (TFLs) proposed in this document.

Any change to the data analysis methods described in the protocol will require an amendment ONLY if it changes a principal feature of the protocol. Any other change to the data analysis methods described in the protocol and the justification for making the change will be described in the clinical study report. Additional exploratory analyses of the data will be conducted as deemed appropriate.

Continuous data will be summarized in terms of the number of observations, mean, standard deviation (SD), median, minimum, and maximum. The minimum and maximum will be reported to the same number of decimal places as the raw data recorded in the database. The mean and median will be reported to one more decimal place than the raw data recorded in the database. The SD will be reported to two more decimal places than the raw data recorded in the database. In general, the maximum number of decimal places reported shall be four for any summary statistic.

Categorical data will be summarized in terms of the number of patients providing data at the relevant time point (n), frequency counts and percentages. Percentages will be presented to one decimal place. Percentages will be calculated using n (the number of observations with non-missing values) as the denominator.

Change from baseline will be calculated as the visit value of interest minus the baseline value. If all baseline values are missing for a particular variable, then the change from baseline and percent change (or percent improvement) from baseline will not be calculated.

All confidence intervals (CIs) and statistical tests will be two-sided unless otherwise specified. P-values which are greater than or equal to 0.001, and less than or equal to 0.999, will be presented to three decimal places. All other p-values which are less than 0.001 will be presented as '<0.001', while p-values greater than 0.999 will be presented as '>0.999'. CIs will be presented to one more decimal place than the raw data.

Age, sex and race will be reported on all by-patient listings unless otherwise specified. Sex will be abbreviated as follows: female (F) and male (M). Race will be abbreviated as follows: American Indian or Alaska Native (AI), Asian (AS), Black or African American (BL), Native Hawaiian or other Pacific Islander (NH), White (WH) and Multiple (MU).

There are five study periods defined in section 7.1 of the protocol:

- Screening Period
- Induction Dosing Period

- Maintenance Dosing Period
- Extension Period- Induction
- Extension Period- Maintenance
- Follow Up Period

Table 1 gives the treatment groups to be displayed for each treatment period and analysis population post implementation of protocol amendment (a). NOTE: “LY3074828” will be included in treatment group names in the statistical reports where possible.

Table 1 Treatment Groups for Each Treatment Period and Analysis Population

Treatment Period	Analysis Population	Treatment Groups	Abbreviation	Between Group comparison (when applicable)	Overall Comparison(when applicable)
Induction Dosing Period	ITT, Safety	600 mg LY3074828 IV 200 mg LY3074828 TDM IV 50 mg LY3074828 TDM IV LY3074828 Total Pbo IV	600 mg IV 200 mg TDM IV 50 mg TDM IV LY T total Pbo IV	600 mg IV vs Pbo IV 200 mg TDM IV vs Pbo IV 50 mg TDM IV vs Pbo IV	600 mg IV 200 mg TDM IV 50 mg TDM IV Pbo IV
Maintenance Dosing Period	Induction Responders	200 SC LY3074828 Q4W 200 SC LY3074828 Q12W LY3074828 Total Pbo SC	200 SC Q4W 200 SC Q12W LY T total Pbo SC	200 SC Q4W vs 200 SC Q12W	No Overall Comparison
Extension Period Induction	All enrolled in Extension Period- Induction	600 mg LY3074828 IV 1000 mg LY3074828 IV Total	600 IV 1000 IV Total	600 mg IV vs 1000 mg IV	No Overall Comparison
Extension Period Maintenance	All enrolled in Extension Period- Maintenance	200 mg LY3074828 SC Q4W	200 SC Q4W	No Between-Group Comparison	No Overall Comparison

Note- Patients who received 600mg IV Extension dosing prior to the protocol amendment will be summarized as 600mg IV. Patients who received 1000mg IV Extension dosing after to the protocol amendment will be summarized as 1000mg IV.

Safety summaries will only compare LY Total to Pbo in Induction.

All summary tables will be presented by treatment group. Where applicable, data will be summarized by treatment group by study visit. Summaries and analyses will be presented

separately for the Induction Dosing Period and the Maintenance Dosing Period. Summaries and analyses will be also presented for the Extension Period.

By-patient listings will be sorted by treatment allocation, site and visit. Numeric data will be listed to the same number of decimal places as recorded on the eCRF. For derived variables, the number of decimal places will be listed as specified. The decimal points will be aligned in the data listings. For the tables and listings in the appendices, "Page x of X" will appear on each page.

By-patient listing will be generated for each SDTM dataset. If necessary, separate listing for derived variables (that are derived from the SDTM datasets) will be generated. Wherever applicable, listings will include the period of the study during which the event or measurement occurred.

Efficacy analyses will be conducted on the Intent-to-Treat (ITT) population. All safety analyses will be conducted on the Safety Population. These populations are defined in section 6.2.

Patients will be analyzed according to the treatment to which they were assigned regardless of any errors of dosing.

All tests of treatment effects will be conducted at a 2-sided alpha level of 0.05 unless otherwise stated. Unless otherwise specified, no multiplicity adjustment will be considered for planned analyses.

For all efficacy and health outcomes analyses, baseline is defined as the last non-missing assessment recorded on or prior to the date of first study drug injection at Week 0 (Visit 2). However, placebo patients who enter the Extension Period will have their baseline reset. Their new baseline will be defined as the last non-missing assessment on or prior to the date of first injection of study treatment at Week EW0 (Extension Visit 1).

Unless otherwise specified, variables will be analyzed in the original scale on which they are measured. However, if it is deemed more statistically appropriate, a transformation, such as to the logarithmic scale, may be applied before analysis. The parametric approach will be employed by default for statistical analysis except when nonparametric analysis, such as by a rank-based method, is assessed to be more fitting.

The primary analysis of categorical (binary) efficacy and health outcome variables will use a logistic regression analysis with treatment, geographic region, and prior biologic experience (prior biologic experience vs prior biologic naïve), and visit (when appropriate) in the model. The odds ratio, the corresponding 95% CIs and p-value, as well as the treatment differences (where appropriate) and the corresponding 95% CIs, will be reported. Secondary analysis will be conducted using an exact Cochran-Mantel-Haenszel test that stratifies by (i.e., controls for) previous biologic use. A Fisher's exact test may be utilized if necessary.

The primary analyses for all continuous efficacy and health outcome variables will be based on the MMRM analysis method. The MMRM analyses will be conducted using a restricted maximum likelihood (REML)-based repeated measures approach. When MMRM is used, the model will include treatment, visit, geographic region, prior biologic experience (prior biologic

experience vs prior biologic naïve), treatment-by-visit interaction, as well as the continuous, fixed covariates of baseline value and baseline value-by-visit interaction. The covariance structure to model the within-patient errors will be unstructured. If the unstructured covariance matrix results in a lack of convergence, the heterogeneous Toeplitz covariance structure, followed by the heterogeneous autoregressive covariance structure, followed by the compound symmetry structure will be used. The first structure to yield convergence will be used for inference. The Newton-Raphson with ridging optimization technique will be used to aid with convergence. The Kenward-Roger approximation will be used to estimate the denominator degrees of freedom and adjust standard errors. Type III tests for the LS means will be used for the statistical comparison; the 95% CI will also be reported. Treatment group comparisons with placebo at Week 12 (Visit 7) and all other appropriate time points will be tested.

Secondary treatment comparisons of continuous efficacy variables at Week 12 and 52 will be made using ANCOVA with treatment, geographic region, prior biologic experience (prior biologic experience vs prior biologic naïve), and baseline value in the model. Type III sums of squares for the least-squares (LS) means will be used for the statistical comparison; the 95% confidence interval will also be reported.

Not all displays and analyses described in this SAP will necessarily be included in the CSR. Not all displays will necessarily be created as a “static” display. Some displays may be incorporated as interactive display tools instead of or in addition to a static display. Any display described in this SAP and not provided in CSR would be available upon request.

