7.1.1. Study Extensions

Subjects who complete the induction period (through Visit 7) but do not have a clinical response (see Section 10.1.2) may choose to participate in the unblinded study extension period following consultation with, and at the discretion of, the investigator. The extension period will consist of induction and maintenance parts that are modified versions of the induction and maintenance periods in the primary study design (Figure AMAC.7.2). For subjects who choose to participate, Extension Visit 1 (Attachment 2) should be planned to occur within 12 days of induction period Visit 7.

During the extension period induction, all subjects are planned to receive 1000 mg LY3074828 IV administered at Extension Weeks 0, 4, and 8 (the dose level and/or frequency of dosing may be reduced based on review of Study AMAC trial data). Subjects should complete all assessments according to the extension period schedule of events (Attachment 2) and should remain on permitted UC concomitant medication according to Section 9.9. Subjects who have a clinical response (Section 10.1.2) at Extension Visit 6 will have the opportunity to continue on extension period maintenance therapy, while nonresponders at Extension Visit 6 will be discontinued from the study.

Subjects who continue into the extension period maintenance treatment are planned to receive unblinded 200 mg LY3074828 administered SC Q4W for 80 weeks. Subjects should complete all assessments according to the extension period schedule of events in Attachment 2, and should remain on permitted UC concomitant medication according to Section 9.9. The dose level and frequency of dosing may be reduced based on review of Study AMAC trial data.

Extension Follow-Up Period (16 Weeks):

A follow-up period will include a visit every 4 weeks for a total of 16 weeks following Extension Week 92 to assess subject safety. Subjects who discontinue the study for any reason during the extension or extension follow-up period will complete the extension period early termination visit (V808).

[figure not shown]

Figure AMAC.7.2. Protocol I6T-MC-AMAC extension period study design.

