2.4. List of Abbreviations

ADA	Anti-Drug Antibodies
AE	Adverse Event
ALT	Alanine aminotransferase
AST	Aspartate aminotransferase
ATC	Anatomical Therapeutic Classification
BMI	Body Mass Index
CSR	Clinical Study Report
eCRF	Electronic Case Report Form
ECG	Electrocardiogram
HLT	High Level Term
IBDQ	Inflammatory Bowel Disease Questionnaire
IRR	Infusion Related Reactions
ITT	Intent to Treat
IC	Informed Consent
IV	Intravenous
IWRS	Interactive Web-Response System
LLN	Lower Limit of Normal
LLT	Lowest Level Term
LSS	Lilly Safety System
LOCF	Last Observation Carried Forward
mBOCF	modified baseline observation carried forward
MedDRA	Medical Dictionary for Regulatory Activities
MMRM	Mixed-Effect Model Repeat Measurement
MRD	Minimum Required Dilution

Msec	Millisecond
Nab	Neutralizing Antibody
NRI	Non-Responder Imputation
OLE	Open-Label Extension
PGI-I	Patient's Global Impressions of Improvement
PGI-S	Patient's Global Impressions of Severity
PK/PD	Pharmacokinetics/Pharmacodynamics
PT	Preferred Term
Q4W	Every 4 Weeks
Q12W	Every 12 Weeks
QNS	Quantity Not Sufficient
QTcF	Corrected QT (Fridericia)
QTcLCTPB	Corrected QT (large clinical trial population based)
RHI	Robarts Histopathology Index
SAE	Serious Adverse Event
SAP	Statistical Analysis Plan
SC	Subcutaneous
SF36	36-Item Short Form Health Survey
SI	International System of Units
SMQ	Standardised Medical Queries
SOC	System Organ Class
TDM	Therapeutic Drug Monitoring
TEAE	Treatment-Emergent Adverse event
UC	Ulcerative Colitis
UCEIS	Ulcerative Colitis Endoscopic Index
WHO	World Health Organization

3. Revision History

SAP Version 2 was approved prior to first unblinding.

SAP Version	Version Date	Comments
Version 1.0	20JUNE2016	Version 1.0 was approved prior to unblinding.
Version 2.0	02JUNE2017	Version 2.0 was approved prior to unblinding.
Version 3.0	11JAN2018	Version 3.0 was approved post unblinding of study.

Revisions Post Final SAP Version 1.0 20JUNE2016

Section	Summary of Changes
2.4	Added Informed Consent (IC)
3	Added approval date for SAP v2.
4.3	Added UCEIS Reference
5.1	
 • Modified definition for prior biologic therapy. • Added Maintenance Rescue criteria at w 52 and beyond • End of maintenance dosing period changed from Week 52 to Week 104. • Study schematics updated to reflect the longer study duration. • Modified the Extension Induction dose to 1000 mg IV from 600mg IV.
5.3	The dose for Extension Period – Induction portion of the study changed from 600 mg to 1000 mg

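### SAP Table 1 lists 600 mg against 1000 mg as an extension comparison, but the groups are non-randomised sequential cohorts split by an amendment, so a difference could not be attributed to dose (minor)

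*SAP*

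**What the plan says.** SAP 6.1, Table 1, sets out the treatment groups and comparisons for each period. In the Extension Period Induction row the between-group entry is "600 mg IV vs 1000 mg IV", and the population is everyone enrolled in that part of the study. The next row, Extension Maintenance, states that there is no between-group comparison.

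The note under the table says how the two groups arise: "Patients who received 600mg IV Extension dosing prior to the protocol amendment will be summarized as 600mg IV", and "Patients who received 1000mg IV Extension dosing after to the protocol amendment will be summarized as 1000mg IV". The SAP revision history (section 3, entry for section 5.1) records the change behind this: "Modified the Extension Induction dose to 1000 mg IV from 600mg IV".

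On allocation, SAP 5.3 says: "Patients entering the Extension Period-Induction portion of the trial will not be re-randomized but will receive 1000 mg LY3074828". Protocol 7.1.1 adds that subjects who complete induction without a clinical response "may choose to participate in the unblinded study extension period following consultation with, and at the discretion of, the investigator".

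For binary efficacy outcomes, the default method in SAP 6.1 is a "logistic regression analysis with treatment, geographic region, and prior biologic experience", with visit added where appropriate. It reports an odds ratio, confidence interval and p-value.

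SAP 6.11.5 treats extension efficacy as exploratory. Its tables of response and remission cover patients originally randomised to LY3074828 and are laid out by original induction arm, not by extension dose.

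**The concern.** A comparison column in a table of treatment groups is normally read as the list of contrasts the programmers will run. Here it names a contrast between two dose levels of the same drug, beside rows whose contrasts come from randomisation. Nothing in the SAP marks this one as non-randomised or descriptive.

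If the contrast were run with the default model, the output would be an odds ratio and p-value labelled 600 mg against 1000 mg. A reader of the study report could take that as evidence on dose in induction non-responders. What it would measure is the difference between an earlier and a later cohort, which includes any dose effect and anything else that changed between the two. The stake is a misleading exploratory result. The test of the primary objective is not touched.

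**Working it through.** The plan gives no sample size, power or expected rate for this contrast. Its one power figure (89%, SAP 5.2) concerns the induction comparisons with placebo and has no bearing here. The check is therefore a reading of the texts and a question of what the model can estimate.

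**Step 1: how a patient comes to be in one group or the other.** By the Table 1 note, the 600 mg group received extension dosing before the amendment and the 1000 mg group after it. By the revision history, one planned dose replaced another. By SAP 5.3, there was no randomisation at extension entry. Group membership is thus settled by when a patient entered the extension.

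**Step 2: what the default model can estimate.** Let D = 1 for 1000 mg and 0 for 600 mg, and let E = 1 for entry after the amendment and 0 for entry before it. The note makes D = E for every patient. Suppose the true model is

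logit(p) = a + b·D + e·E + region + previous biologic use.

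Substituting E = D gives

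logit(p) = a + (b + e)·D + region + previous biologic use.

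The fitted treatment coefficient estimates b + e. The dose effect b cannot be recovered unless e = 0 is assumed, and a larger sample does not change that.

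**Step 3: whether a further covariate would help.** Adding E makes the model collinear. Replacing E with calendar date helps only if some patients started the two doses at the same time. The documents do not say whether sites adopted the amendment on different dates. If they did, dose among concurrent entrants would follow site, and one confounder would replace another.

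**Step 4: original induction arm.** The Table 1 population pools patients from placebo, 50 mg, 200 mg and 600 mg induction. The default model has no term for that arm. Adding one would remove differences in arm mix but would leave the result of step 2 unchanged.

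**Step 5: whether the plan really calls for a test.**
- For: SAP 6.1 promises analyses as well as summaries for the extension and sets a two-sided 0.05 level by default. The adjacent row shows that the authors had a way to decline a comparison.
- Against: the column heading limits its entries to where they apply, the note speaks only of summarising patients, and no section names an endpoint or model for this contrast.

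The SAP leaves it open.

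**Step 6: agreement with SAP 6.11.5.** Table 1 groups all extension enrollees by extension dose. Section 6.11.5 groups the LY3074828-randomised enrollees by original induction arm. The two do not describe the same display.

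**The case against.** The strongest reply is that no test has been shown to exist. The column is qualified, and no section attaches an endpoint or p-value to 600 mg against 1000 mg. The repeated-measures text in SAP 6.1 names comparisons with placebo, and the extension has no placebo arm (Protocol 7.2). The note under Table 1 confines safety comparisons to all LY3074828 against placebo in induction. The extension efficacy tables in 6.11.5 are already laid out by original induction arm and leave out patients first randomised to placebo. The amendment-based definition is disclosed directly under the table. All of this stands, and it is why the point is minor. It does not explain why the cell is there, and it does not make the contrast interpretable if someone runs it.

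A reader might go further in three ways that the documents do not support:
- *That the two cohorts differ in sites or in mix of original arms.* No section shows this. Induction allocation was 1:1:1:1, which gives no evident reason for the arm mix to shift at the amendment.
- *That open-label dosing biases the contrast.* The extension is unblinded at both doses, so it does not by itself distinguish the groups.
- *That the outcome is on a different scale in the two groups.* Baseline is reset for ex-placebo patients at either dose, so this would matter only if their share differed. Endoscopic remission has no baseline term at all.

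**Conclusion.** The point holds as a minor correction to the analysis plan. Table 1 lists a dose contrast between non-randomised, sequential cohorts. Dose coincides with position relative to the amendment, and the default model cannot separate them. Any odds ratio or p-value from the contrast would therefore describe cohort and dose together.

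This rests on the SAP's own definition of the groups and on the absence of randomisation at extension entry. It needs no assumption that the cohorts actually differ. The size of any distortion cannot be given, because the documents report no extension group sizes or response rates. A numerical illustration would depend wholly on invented inputs.

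It would be wrong to conclude that a p-value is certain to be produced, that a bias has been demonstrated, or that the trial's dose conclusions are at risk. The contrast is exploratory, lies outside the testing sequence in SAP 6.6, and bears on no primary or secondary conclusion.

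**What to change.** In SAP Table 1, replace the between-group entry for Extension Period Induction with the no-comparison wording already used for Extension Maintenance. Keep the 600 mg and 1000 mg extension groups as descriptive columns, shown within original induction arm. Add a sentence to the table note saying that the groups are non-randomised, were formed by the amendment, and do not support inference about dose. Align 6.11.5 with this, including whether patients first randomised to placebo appear as their own group, so that the table and the section describe the same display.

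The cost is one table cell, one sentence and, at most, one exploratory p-value. Splitting two doses by four original arms gives 2 × 4 = 8 cells, some of which may be small. That is acceptable for a descriptive display. No data collection, sample size or primary analysis changes.

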6.3. Adjustments for Covariates

The randomization at the beginning of the Induction Period is stratified by previous biologic therapy: previous exposure to biologic therapy for treatment of UC, biologic naïve to biologic therapy for treatment of UC. Unless otherwise specified, all efficacy and health outcome analyses will include the stratification factors in the model.

The re-randomization at the beginning of the Maintenance Period of patients who took LY3074828 during the Induction Period and were responders at Week 12 (Visit 7) is stratified by the Week 12 level of clinical response: Clinical Remission or Clinical Response. Unless otherwise specified, all efficacy and health outcomes analyses using the Maintenance Dosing Period Primary population will include the re-randomization factor of Week 12 level of response in the model.

Unless otherwise specified, analyses will be performed utilizing the methodology and covariates described in section 6.1.

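### For continuous outcomes, the Q4W vs Q12W models adjust for the Week 0 value but not the Week 12 value measured just before re-randomisation, which costs precision without causing bias

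*SAP*

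**What the plan says.** SAP 6.1 sets one baseline: "For all efficacy and health outcomes analyses, baseline is defined as the last non-missing assessment recorded on or prior to the date" of the first study drug administration at Week 0. It allows one exception: "placebo patients who enter the Extension Period will have their baseline reset". Responders re-randomised to a maintenance regimen get no new baseline.

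That value is the covariate in both continuous models. The MMRM includes treatment, visit, region and prior biologic experience, "as well as the continuous, fixed covariates of baseline value and baseline value-by-visit interaction". The ANCOVA sentence reads "Secondary treatment comparisons of continuous efficacy variables at Week 12 and 52 will be made using ANCOVA with treatment, geographic region, prior biologic experience", followed by the baseline value. Binary outcomes use a "logistic regression analysis with treatment, geographic region, and prior biologic experience", with visit where appropriate and no baseline score.

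For the Maintenance Period, SAP Table 1 gives the between-group comparison as "200 SC Q4W vs 200 SC Q12W" in the Induction Responders population. SAP 6.3 says that "analyses using the Maintenance Dosing Period Primary population will include the re-randomization factor of Week 12 level of response in the model". That factor has two levels, remission or response. Table 2 does not define the population named there. SAP 6.11.4, on the maintenance endpoints, refers only to 6.1, whose model lists omit the factor.

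In the protocol's Attachment 1, endoscopy, the full Mayo score, IBDQ and SF-36 are collected at Visit 7, and re-randomisation is at Visit 8.

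**The concern.** Q4W vs Q12W is the trial's second randomised comparison. According to protocol 7.2 it is meant to inform the choice of maintenance regimen for later studies. Only induction responders to LY3074828 enter it, and neither document gives a sample size or power for it.

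The natural covariate for a randomised comparison is the value of the outcome just before that randomisation, here the Visit 7 value. It will usually predict Week 52 better than a value taken 12 weeks earlier and before induction treatment. The plan uses the earlier value and reduces the later one to a two-level factor. Because the wording in 6.3 points to an undefined population, a programmer working from 6.1 might omit even that factor. What is at stake is the width of the confidence intervals for continuous outcomes in a small comparison.

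The protocol follows the better principle elsewhere: in 12.2.8 the maintenance baseline for safety variables is the last induction value.

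**Working it through.** **1. The plan's own figure.** The only power statement (protocol 12.1, SAP 5.2) is 89% for each induction comparison: 30% vs 7.5%, 60 per arm, two-sided 0.05. With the pooled chi-square formula, z = (0.225√60 − 1.96√(2 × 0.1875 × 0.8125)) / √(0.30 × 0.70 + 0.075 × 0.925) = (1.743 − 1.082)/0.529 = 1.25, which is 89.4%. It reproduces, but says nothing about Q4W vs Q12W.

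**2. Inputs for the covariate question.** None is in the documents, so all are assumptions:
- r0, the correlation of Week 0 with Week 52: 0.2-0.3
- r1, the correlation of Week 12 with Week 52: 0.4-0.6
- r01, the correlation of Week 0 with Week 12: 0.2-0.4
- c, the correlation of the remission indicator with the Week 12 value: 0.48 for a loose link. For a tight link, remission is a clean cut of a normal Week 12 value with 35% in remission, so c = 0.370/√(0.35 × 0.65) = 0.78.

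**3. Formula.** For a standardised Week 52 value and two covariates with correlations a and b to it and r to each other, the residual variance is V = 1 − (a² + b² − 2abr)/(1 − r²). Remission is taken to add nothing once the Week 12 value is known, so its correlations are c·r1 with Week 52 and c·r01 with Week 0. The gain from adding the Week 12 value, as extra patients for the same standard error, is V(without)/V(with) − 1. Since Week 0 is in every model, using change from Week 0 as the outcome gives the same V.

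**4. Results before restricting to responders.**

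| | Case A: r0 0.2, r1 0.4, r01 0.2 | Case B: r0 0.3, r1 0.6, r01 0.4 |
|---|---|---|
| V, Week 0 + Week 12 | 1 − 0.168/0.96 = 0.825 | 1 − 0.306/0.84 = 0.636 |
| V, Week 0 only | 0.960; gain 16% | 0.910; gain 43% |
| V, Week 0 + stratum, c = 0.48 | 0.930; gain 13% | 0.855; gain 34% |
| V, Week 0 + stratum, c = 0.78 | 0.879; gain 7% | 0.755; gain 19% |

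Pairing the weakest Week 0 with the strongest Week 12 correlation (0.2, 0.6, r01 = 0.2) gives 0.887/0.633 − 1 = 40% at c = 0.48.

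**5. Restriction to responders.** Only Week 12 responders are re-randomised, which narrows the spread of Week 12 values and so their predictive value. Simulations with the stratum in both models and responders only gave about 3-33%:
- Case B with remission a clean cut, and responders selected on improvement from Week 0: the gain falls from 19% to 11%.
- Responders taken as the best half on the Week 12 value and remission as a clean cut of it: 2-7%.
- The highest gains, about a third, arise when response and remission track the outcome only loosely.

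Rounded over these settings, the gain is roughly 3-35%.

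**6. Which analyses are affected.**
- SAP Table 3: all six maintenance endpoints are binary, and their logistic model has no baseline score. Not affected.
- Histology scores (SAP 6.14.9): unpaired t-test of each active arm against placebo, no covariate. Not affected.
- CRP (SAP 6.14.7): summaries, graphs and correlations. Not affected.
- SF-36 (SAP 6.12.1.1): ANCOVA against placebo through Week 24. Affected only if a Q4W vs Q12W model is also fitted under 6.1.
- UCEIS and partial Mayo (SAP 6.11.5): summaries and graphs. Affected only through the general 6.1 text.
- IBDQ: falls under the general 6.1 model. Affected.

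**The case against.** The strongest reply is that nothing here is wrong, only less efficient. Re-randomisation makes the comparison valid whichever earlier value is used. The maintenance period is described as exploratory, the SAP already brings in Week 12 status through the stratum, and 6.1 permits further exploratory analyses. The secondary maintenance efficacy endpoints are all binary and would not change. All of this stands, and it limits the point to a precision gain for a few continuous outcomes.

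The reply about size also stands in part. The gain rests wholly on assumed correlations. Remission is built from Mayo subscores, so for Mayo-based outcomes the stratum may already capture much of the Week 12 information, and analysing responders only reduces the gain further.

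It does not dispose of the point. The Visit 7 value precedes re-randomisation, so adjusting for it introduces no bias, and it is already collected. The two-level factor is also not securely in the models, given the undefined population in 6.3 and the reference to 6.1 alone in 6.11.4.

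**Conclusion.** The point holds as a loss of precision for continuous Q4W vs Q12W models fitted under SAP 6.1: clearly for IBDQ, and for Mayo-based, UCEIS or SF-36 scores where such a model is fitted. Under the assumed correlations, adding the Week 12 value to a model with the stratum is worth roughly 3-35% more patients. The structural facts are firm; the size is not.

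A reader might infer three stronger conclusions that the documents do not support:
- That the comparison is biased. Both values precede the second randomisation, so either adjustment is valid.
- That the whole maintenance analysis suffers. The Table 3 endpoints, the histology t-tests and the CRP summaries do not use a Week 0 covariate for this comparison.
- That the loss is a firm 13-34%, or a set number of patients per arm. The range 13-34% is what the table gives for Cases A and B at c = 0.48 without restriction to responders. The documents state neither the correlations nor the number to be re-randomised.

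**What to change.** In SAP 6.1 and 6.3, state that every continuous Q4W vs Q12W model is fitted in the Induction Responders population and includes the Week 12 (Visit 7) value of the same variable, with its visit interaction in the MMRM, and the Week 12 remission stratum. Keep change from Week 0 as the displayed outcome. Replace the undefined population label in 6.3 with Induction Responders, and have 6.11.4 cite 6.3 as well as 6.1 so that the stratum is not overlooked.

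The cost is a few sentences of SAP text and one covariate already scheduled for collection at Visit 7. No visit, sample or endpoint changes.
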